Our institution has been using RiaSTAP on this high-risk patient population since April 2013. In a separate, retrospective analysis our group has compared a group of 50 patients who received RiaSTAP with 50 age, diagnosis and procedure matched patients prior to April 2013. Our analysis demonstrates that there is a statistically significant reduction in the need for FFP and cryoprecipitate, without an increase in thromboembolic events, when RiaSTAP is used at a dose of 70 mg/kg.¹⁵

Criteria For Subject Selection

Number of subjects: 30

Gender of subjects: There are no gender-based enrollment restrictions for this study. Gender distribution should reflect the gender distribution of the patient population and the gender distribution of Congenital Heart Disease (CHD) in general which is slightly skewed towards male patients in a 60:40 ratio of males to females.

Age of Subjects: Age will range from full term (at least 37 weeks gestational age) newborns to 12 months old, inclusive.

Racial and Ethnic Origin: There are no racial and ethnic restrictions for this study.

Inclusion Criteria: All neonatal and infant cardiac patients presenting for open-heart surgery at Nicklaus Children's Hospital will be eligible for enrollment in the study.

Exclusion criteria: Patients who fall outside of the age range for the study will be excluded. Patients known to have had an anaphylactic or severe reaction to the drug or its components will not be enrolled. At the time of the rewarming ROTEM, any patient with a FIBTEM MCF > 15 mm, will be excluded.

Vulnerable subjects: Patients in the study population are neonatal and infant cardiac surgical patients and are considered vulnerable subjects.

Methods and Procedures

Randomization:

We plan to enroll 30 neonates and infants scheduled for elective cardiac surgery. Patients will be randomized to one of two groups with 15 patients in each group; Group 1 will receive an infusion of RiaSTAP, right after the termination of CPB at a dose of 70 mg/kg and

Group 2 will receive a placebo of Normal Saline 0.9% (NS) during the same time period. The volume of NS will be calculated to be the same volume that would be used IF the patient were receiving RiaSTAP. This will be the only difference between the groups.

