Both Groups will receive the normal standard of care both before and especially after this event. This will be the only event that is different for the two groups. To avoid selection bias, the Pharmacy will perform the randomization using Research Randomizer. Briefly, for each patient, a randomly generated integer between 1-30 will be produced. If the number is even, the patient will be assigned to Group 1. If the number is odd, the patient will be assigned to Group 2. The randomization process and schedule will be provided by the Principal Investigator's office, but the actual patient assignment will be done by Pharmacy.

All operating room and ICU personnel will be blinded to the patient's Group assignment. The only persons who will have access to the identity of the Group assignment from the time of randomization until 24 hours after surgery will be members of the Pharmacy staff. NONE of these individuals will be involved in patient care. The DSMB will be unblinded AFTER the study treatment period concludes (24 hours after surgery).

Endpoints:

Primary efficacy endpoints will be estimated as follows:

- postoperative bleeding (EBL) during the first 24 hours (hr) after surgery (cc/kg),
- the identity and total volume of transfused blood products (cc/kg) given in the peri-operative period, separated out into its components,
- hemoglobin concentration 2 hr. and 24 hr. after surgery and
- effects of fibrinogen infusion on global hemostasis 2 hr. and 24 hr. after surgery (PT, PTT, INR, fibrinogen level, platelet count and ROTEM analysis).

Post-operative period begins after the patient leaves the operating room. The need for Factor VII use and dose will also be included as a primary end point. Factor VII is typically used only if there is profuse bleeding not amenable to component transfusion therapy.

Secondary end points will include:

- the number of post-op hours requiring ventilator support,
- Length of Stay (LOSH) in the hospital,
- Length of Stay (LOS ICU) in the Cardiac Intensive Care Unit (CICU) and
- the need for re-exploration for bleeding within the first 12 hours.

The primary safety endpoints that will be monitored are the presence of a clinical adverse events. Clinical adverse events (AEs) are defined as any clinical signs of central or peripheral thromboembolism, respiratory or circulatory failure, or allergic reactions during hospital stay. It will also include infection with a blood-borne pathogen.

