Thromboembolic phenomenon will include catheter and/or vessel occlusion. Any signs or symptoms of thromboembolism will prompt a Doppler ultrasound examination to confirm the diagnosis. All patients will be monitored for AEs until discharge.

Anesthetic Management:

Standard non-invasive monitors will be employed including Electrocardiogram (EKG), Non-invasive blood pressure (NIBP), Pulse Oximetry (SaO_2), capnography, and Near Infrared Spectroscopy (NIRS).

For patients greater than six months of age, premedication with midazolam will be used. Dose will be 1 mg/kg Per Os (PO), with a maximum of 20 mg. Anesthesia will be induced with Propofol 2 mg/kg or fentanyl 5 mcg/kg, if the patient already has an indwelling IV catheter. Otherwise an inhalational induction with Sevoflurane 5% will be done. Anesthesia maintenance will be with Sevoflurane and dexmedetomidine 1 mcg/kg/hr. No more than 10 mcg/kg of fentanyl will be used. Once the patient is anesthetized and intubated a Foley catheter will be placed along with an Arterial line (A-line) and a double lumen Central venous line (CVL). Hemodynamics will be maintained by adjusting the Sevoflurane concentration in increments of 0.5% to maintain blood pressure within 20% of baseline. Propofol 0.5 mg/kg will also be used for this purpose.

Cardiopulmonary Bypass (CPB) Management:

After purse strings sutures are placed, heparin 300 International Units (IU) will be administered by the surgeon directly into the right atrium (RA) in order to maintain an ACT greater than 400 seconds. After CPB, the heparin will be reversed by the administration of protamine (1 mg protamine/100 IU of residual heparin activity as measured by the Medtronic Hepcon) to an ACT of <130 s. The CPB circuit included a membrane oxygenator and centrifugal pumps. Standard non-pulsatile CPB technique with moderate hypothermia (bladder temperature 28–30°C) or deep hypothermia (bladder temperature 18–20°C) and hemodilution will be used depending on the surgical repair. Cardioprotection will be achieved with antegrade cold blood cardioplegia. Weaning off CPB will be performed after rewarming to a bladder temperature of at least 36°C. We will use the Medtronic Hepcon Hemostasis Management System Plus to optimize and monitor heparin and protamine dosing.

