Primary efficacy endpoints will be postoperative bleeding during the first 24 hours (hr) after surgery (cc/kg), the total volume and identity of transfused blood products (cc/kg), hemoglobin concentration 2 hr. and 24 hr. after surgery and effects of fibrinogen infusion on global hemostasis 2 hr. and 24 hr. after surgery (PT, PTT, INR, fibrinogen level, platelet count and ROTEM analysis). Secondary end points will include the number of post-op hours requiring ventilator support, Length of Stay (LOS) in the Cardiac Intensive Care Unit (CICU), the need for re-exploration for bleeding within the first 12 hours, and LOS in the hospital. The need for Factor VII use and dose will also be included.

The primary safety endpoint is a clinical adverse event. Clinical adverse events are defined as:

1. Any clinical signs of central or peripheral thromboembolism. This will then be confirmed by Doppler ultrasound. Assessments will be made once per shift (once every eight hours)
2. Respiratory or circulatory failure. Parameters of respiration, like respiratory rate (RR), end-tidal CO₂ (ETCO₂) and circulation, like heart rate (HR), rhythm, blood pressure (BP), arterial oxygen saturation (SpO₂) are monitored continuously while in the ICU. Respiratory failure will be defined as the need for reintubation after extubation. Circulatory failure will be defined as cardiac arrest.
3. Allergic reactions during hospital stay. These will include signs or symptoms like urticaria, wheezing, angioneurotic edema, and anaphylaxis.
4. Infection with a blood borne pathogen. Manifestation of an infection with a blood borne pathogen is unlikely to occur during the study treatment period, which ends 24 hours after the end of surgery. If this were to occur, it would not manifest itself for weeks or even months.

Patients will be assessed once per shift (once every eight hours) for signs of thromboembolism. Any evidence of thromboembolism will warrant a vascular ultrasound to assess the integrity of the vessel.

Adverse events will be monitored until discharge.

All patients will be assessed for signs and symptoms of thromboembolism, per routine care. Specifically, patients will be assessed for signs and symptoms of central and arterial

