line thrombosis. These include edema, leg pain and tenderness, erythema, and discoloration for venous thrombosis, as well as loss of distal peripheral pulses, pain, pallor, paresis, paresthesias, decreased skin temperature for arterial thrombosis. If any of these signs and symptoms appear, Doppler Ultrasound examinations of the affected area will be performed.

The Safety Team, which consists of the Cardiac Intensive Care Unit physicians, will evaluate each event when it occurs; they will not be blinded to patient assignment after 24 hours. Please see safety assessments and timing below. These represent minimums as prescribed by the protocol. Assessments may be more frequent (See table 1).

Stopping Criteria:

A statistically significant increase in thromboembolic phenomenon between Group 1 and Group 2 will trigger a stop in enrollment. This will be monitored by the Safety Team.

Table 1: Assessments

Assessment	Timing in OR	Timing in ICU
EBL	q 15 min	hourly
ROTEM	q 30 min as needed	hours 2 and 24, or as needed hourly until bleeding ceases
peripheral thromboembolism	N/A	q8 hrs, or as needed
hemoglobin	as needed	hours 2 and 24
PT/PTT, platelets, fibrinogen	prior to surgery if not previously done	hours 2 and 24

Schedule of Events

	Pre-Operative	Intraoperative	2 hours Post-Operative	24 hours Post-Operative	When occurs	60 ± 14 days
Informed Consent/Assent	x					
Eligibility Assessment	x					

Demographic Data	X					
Medical History	X					
Baseline Assessment ¹	X					
Body Weight and Height	X					
Concomitant Medications ⁴	X	X				
Randomization		X				
Administration of Study Drug		X				
Pharmacy Prep of Study Drug		X				
Laboratory Studies ²	X		X	X		
Adverse Events		X	X	X	X	X
Surgical and Cardiopulmonary Bypass Data ³		X				
Estimated Blood loss (EBL) ^{5,6}					→	
ROTEM Analysis ^{9,11}	X	X ^{7,10}	X	X	X ⁸	
Identification of total transfused blood products ¹²				X		
Thromboembolic Assessment ¹³			→		X	
Factor VII					X	
Length of Stay ICU and Hospital					X	
Mechanical ventilation duration					X	
Need for Re-exploration first 12 hours			X	X		
Phone assessment						X

1. Assessment includes allergies, diagnosis, procedure(s)
2. Laboratory collection and assessment includes CBC, prothrombin time (PT), international normalized ratio (INR), partial thromboplastin time (PTT), fibrinogen level. Pre-Operative includes complete platelet count, and electrolyte profile.

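### The only formal thromboembolism stopping trigger, a significant difference between the groups, is insensitive with 30 patients; add a DSMB pause-and-review trigger beside it

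*Combined protocol and SAP*

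**What the plan says.** - **Trigger.** Stopping Criteria: "A statistically significant increase in thromboembolic phenomenon between Group 1 and Group 2 will trigger a stop in enrollment". The next sentence assigns it: "This will be monitored by the Safety Team". No other passage states a criterion for stopping enrollment on thromboembolism.
- **Who applies it.** Patient Assessment: "The Safety Team, which consists of the Cardiac Intensive Care Unit physicians, will evaluate each event when it occurs". That team is unblinded to assignment after 24 hours.
- **Test.** Statistical Analyses names Fisher's exact test for categorical treatment–placebo comparisons, with significance at p ≤ 0.05. It does not say whether this governs the stopping decision. Neither section states sidedness, look times for the trigger, or an adjustment for repeated looks.
- **Other oversight.** Safety Monitoring has safety data reviewed after 10, 20 and 30 enrolled, without naming the reviewing body or a threshold. Randomization mentions a DSMB: "The DSMB will be unblinded AFTER the study treatment period concludes (24 hours after surgery" (the closing bracket follows in the text). It gives the DSMB no part in the stopping rule.
- **Allocation.** Randomization says: "Patients will be randomized to one of two groups with 15 patients in each group". It then describes a random integer drawn for each patient: "If the number is even, the patient will be assigned to Group 1". If the draws are independent, group sizes can differ from 15.
- **Event definition.** Endpoints: "Thromboembolic phenomenon will include catheter and/or vessel occlusion". Patient Assessment: "Any evidence of thromboembolism will warrant a vascular ultrasound to assess the integrity of the vessel".

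**The concern.** Risk/Benefit Assessment lists thrombotic episodes as the most severe adverse reactions seen with the product, and the patients are newborns and infants. A rule that needs a significant difference before it acts asks a great deal of 30 patients. With few events, Fisher's test reaches p ≤ 0.05 only when the split is nearly complete. If the rule is followed as written, enrollment could run to its end under a substantial excess of thrombosis without the one formal trigger being met. Any earlier pause would rest on judgement for which the protocol gives no threshold. The 30-patient review comes when enrollment is complete, so it cannot stop it.

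**Working it through.** The plan states no event rate, power or operating characteristic for the rule, so it has no figure to reproduce.

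**Inputs.** From the documents: 30 patients; Fisher's exact test at p ≤ 0.05; allocation either 15/15 or an independent 50:50 draw for each patient; reviews at 10 and 20; evaluation of each event. Assumed: the event rates; one- and two-sided tests, both run because sidedness is not stated; and each outcome known before the next patient enrolls, which favours the rule.

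**Step 1: how many events are needed.** For *a* events among *n1* in Group 1 and none among *n2* in Group 2, one-sided p = C(n1, a) / C(n1+n2, a). With equal groups and no Group 2 events, the two-sided p is twice this.

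- 10 patients, 4/5 vs 0/5: 5/210 = 0.024 one-sided, 0.048 two-sided. Fires. (5/5 vs 1/5 also fires, two-sided p = 0.048.)
- 20 patients, 5/10 vs 0/10: 252/15504 = 0.016 one-sided, 0.033 two-sided. Fires.
- 20 patients, 4/10 vs 0/10: 210/4845 = 0.043 one-sided, 0.087 two-sided. Fires one-sided only.
- 15 per group, 5 vs 0: 3003/142506 = 0.021 one-sided, 0.042 two-sided. Fires.
- 15 per group, 4 vs 0: 1365/27405 = 0.0498 one-sided. Fires one-sided only.

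Unequal groups move the threshold:

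- 3/8 vs 0/12: 56/1140 = 0.049. The opposite extreme, 220/1140, is more probable and so is not added. Fires either way.
- 5/12 vs 0/8: 792/15504 = 0.051 one-sided; adding the opposite tail, (792+56)/15504 = 0.055 two-sided. Does not fire.

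**Step 2: how often it fires.** Let the state be (n1, n2, x1, x2), the group sizes and event counts. Each new patient joins Group 1 with probability 1/2 (independent draw) or (15 − n1)/(30 − n1 − n2) (forced 15/15), and has an event at that group's rate. At each look, the probability of states with p ≤ 0.05 and a higher Group 1 rate is added to the firing total and removed. This is exact enumeration, run through patient 29, the last point at which a stop can prevent an enrollment. Silence = 1 − firing probability.

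Firing probabilities:

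| Looks | Rates | Draw, 2-sided | Draw, 1-sided | 15/15, 2-sided | 15/15, 1-sided | Silent |
|---|---|---|---|---|---|---|
| 10, 20 | 20% vs 5% | .046 | .057 | .044 | .060 | 94–96% |
| 10, 20 | 30% vs 5% | .148 | .177 | .151 | .190 | 81–85% |
| 10, 20 | 40% vs 5% | .313 | .360 | .325 | .383 | 62–69% |
| 10, 20, each event | 20% vs 5% | .115 | .137 | .121 | .149 | 85–89% |
| 10, 20, each event | 30% vs 5% | .317 | .368 | .339 | .391 | 61–68% |
| 10, 20, each event | 40% vs 5% | .564 | .623 | .590 | .648 | 35–44% |

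The ranges therefore span sidedness as well as allocation. Two-sided alone at 30% vs 5%, with looks at 10, 20 and each event, gives 66–68%.

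**Step 3: sensitivity.** Testing after every patient gives 81–85%, 55–62% and 30–37% silent at the three rate pairs. With a 10% control rate and looks at 10, 20 and each event, silence is 73–79% at 30% vs 10% and 50–58% at 40% vs 10%. If looks at patient 30 are also counted (10, 20, 30 and each event), silence at 30% vs 5% is 52–64%.

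**Step 4: false alarms.** With equal rates of 5%, 10%, 15%, 20% and 25%, looks at 10, 20 and each event, and independent draws, two-sided Fisher fires in 0.2%, 0.9%, 1.7%, 2.5% and 3.1% of trials. One-sided Fisher spans 0.2–4.1%.

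**The case against.** **The test is not wholly unspecified.** A reader might infer that no test is named at all. The documents do not support that: Statistical Analyses gives Fisher's exact test and p ≤ 0.05, and the word increase gives a direction. What is missing is sidedness, look times, repeated-look handling and a link between the two sections.

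**Oversight is wider than the trigger.** A reader might infer that patients are protected by nothing else. The plan has checks every eight hours, Doppler confirmation, event-by-event evaluation, reviews at 10 and 20, and a DSMB. Nothing bars any of these from leading to an earlier pause, and a DSMB charter, if one exists, is not among the supplied documents. This stands: the finding concerns the formal trigger, not trial safety as a whole.

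**The rates are assumed.** The Background calls the thrombotic risk apparently low, and the institution's retrospective comparison of 50 treated and 50 matched patients found no increase in thromboembolic events. The Background also cites an adult review reporting more neurological thromboembolic complications and renal failure. No rate is given, so no single silence figure can be treated as established. At 40% vs 5% with event-driven looks the trigger fires in most trials.

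**Thirty patients limit any rule.** This stands too. A looser rule gains sensitivity by accepting weaker evidence, and no comparison at matched false-alarm rates was made. The figures therefore do not show that a Bayesian rule is more efficient than Fisher's test, or that it should replace it.

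**Conclusion.** The concern holds for the trigger as written. Under Fisher's test at p ≤ 0.05 it stays silent in most trials at 20% vs 5% and at 30% vs 5% for every sidedness, allocation and look schedule checked. With looks at 10 and 20 only, it also stays silent in most trials at 40% vs 5%. These results rest on assumed event rates, on Fisher's test governing the stopping decision, and on outcomes known at once; delayed events would make the rule less sensitive still. False alarms of about 0.2–4% leave room for a more sensitive early warning. The documents do not support saying that the trial lacks safety oversight, or that the significance stop must go. This is a cheap improvement to the monitoring plan.

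**What to change.** Keep the significance stop, stating its sidedness, look times and responsible body. Add a prespecified trigger that pauses enrollment for review, applied by the DSMB that the protocol already names, and checked at 10 and 20 patients and after each confirmed event. State its probability of triggering under the allocation actually used and over a range of background rates. The DSMB sets the cut-off.

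For illustration only: pause at three or more Group 1 events with posterior probability ≥ 0.90 that the Group 1 rate is higher (uniform priors). With equal groups of up to 15 this pauses at 3 vs 0. With independent draws and looks at 10, 20 and each event, it pauses in 39%, 68% and 87% of trials at 20%, 30% and 40% vs 5%. Two-sided Fisher at the same looks fires in 11%, 32% and 56%. The illustration still misses about a third of trials at 30% vs 5%.

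Cost: protocol and charter wording, with no added patients or procedures. The illustration pauses unnecessarily in about 2%, 7%, 11%, 15% and 18% of trials at equal rates of 5%, 10%, 15%, 20% and 25%. The higher background rates cannot be dismissed, because catheter and vessel occlusion count as events and any sign prompts ultrasound. The gain comes from a looser evidence standard, which is acceptable for a pause and review rather than a permanent stop.

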Patients under 10 kg in body weight will have the CPB pump primed with one unit of Packed Red Blood Cells (PRBC) and 200 cc Fresh Frozen Plasma (FFP). In patients over 10 kg a pure crystalloid prime will be used. Target hemoglobin (Hg) while on CPB will be 9 gm/dL, but the transfusion trigger for additional units of PRBC will be 7 gm/dL.

Drug protocol:

The following laboratory studies will be obtained prior to surgery: Complete Blood Count (CBC), Prothrombin time (PT), International Normalized Ratio (INR), Partial Thromboplastin time (PTT), Platelet count, and a Fibrinogen level; an electrolyte profile will also be done. An Activated Clotting Time (ACT) and a Thromboelastometry analysis [REDACTED], a device that assesses the viscoelasticity of whole blood and other parameters, will be done after an A-line is placed (Figure 1).

A blood products transfusion algorithm was developed based on four previous studies published in the literature, modified for pediatrics¹⁶¹⁷¹⁸¹⁹ (Figure 2). Blood is measured in the cell saver reservoir and the suction canister every fifteen minutes while in the OR. Clinically significant bleeding, requiring treatment, will be defined as a rate in excess of 10 cc/kg/hr calculated every 15 minutes while in the OR. Calculations will be done every 60 minutes in the CICU.

After rewarming, but prior to the termination of CPB a ROTEM analysis will be done. Platelets or FFP will be administered at this time, while still on CPB, if the ROTEM results indicate a deficiency of either component. Then immediately after the termination of CPB, RiaSTAP or NS will be administered depending on the group assignment. Then, as per routine care, a ROTEM analysis and fibrinogen level will be assessed and the transfusion algorithm will be continued. *If the ROTEM indicates a fibrinogen deficiency, cryoprecipitate will be given.* Thereafter, as per routine care, a ROTEM analysis will be done at least every 30 minutes while in the OR or sooner at the discretion of the OR team. Once the patient leaves the OR a ROTEM will be done at least every 60 minutes for the first six hours or until clinically significant bleeding has stopped, whichever comes first; ROTEMs can be done more frequently at the discretion of the ICU staff caring for the patient. The blood products transfused after separation from CPB will be based on the protocol below (Figure 3). Dosing amounts of the required component therapy will be based on the formula below:

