3. Time in/out, sternal closure time, bypass start/stop time, total bypass time, total cross clamp time, total regional low perfusion time, blood components administered for patients under 10 kg in body weight, and pure crystalloid prime for patients over 10 kg in body weight, activated clotting time (ACT), thromboelastometry analysis after A-line assessment.
4. During intraoperative period concomitant medications include anesthesia induction medication, heparin, and protamine.
5. Estimated blood loss will be assessed every 15 minutes while in the OR and every 60 minutes in the CICU. Clinically significant bleeding defined as a rate in excess of 10 cc/kg/hr.
6. Total EBL at 24 hour time point.
7. Prior to Termination of CPB
8. If bleeding occurs
9. If fibrinogen deficiency noted on ROTEM, administer cryoprecipitate
10. Every 30 minutes as routine or sooner as per OR team discretion.
11. Assess post-operatively for every hour for 6 hours or until clinically significant bleeding ceases and additionally as per ICU team's discretion.
12. Includes total prime, total CPB, total Anesthesia, total CICU, total platelets, total PRBC, total FFP, total Cryo, total cell saver.
13. Assess every 8 hours central and arterial line for signs and symptoms. Thrombosis including edema, leg pain and tenderness, erythema, and discoloration for venous thrombosis, loss of distal peripheral pulses, pain, pallor, paresis, paresthesias, decreased skin temperature for arterial thrombosis. Confirmed by Doppler Ultrasound. Report when occurs.
14. Any untoward event reported from the time subject signs consent. Should be reported as soon as the study team becomes aware.

Data Analysis and Data Monitoring

Safety Monitoring

For the safety monitoring, adverse events will be documented. Aggregate and individual subject data related to safety, data integrity and overall conduct of the trial will be reviewed after enrollment of 10, 20 and 30 subjects.

Methods to Minimize Bias

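### The primary transfusion volume does not start at study drug, and its only itemisation includes the bypass prime, which can add weight-driven noise to the FFP and PRBC comparisons

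*Combined protocol and SAP*

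**What the plan says.** - **Endpoint.** The Endpoints section lists as primary "the identity and total volume of transfused blood products (cc/kg) given in the peri-operative period, separated out into its components". The plan defines when the post-operative period begins but never defines the peri-operative one. Patient Assessment repeats the endpoint with no window at all.
- **Content.** The Schedule of Events row for total transfused products is marked in the 24-hour column and points to footnote 12: "Includes total prime, total CPB, total Anesthesia, total CICU, total platelets, total PRBC, total FFP, total Cryo, total cell saver".
- **Recording.** The Drug protocol section has red cells, FFP, cryoprecipitate and platelets recorded in cc/kg over the hospital stay.
- **Prime.** Under CPB Management, the pump for patients under 10 kg is "primed with one unit of Packed Red Blood Cells (PRBC) and 200 cc Fresh Frozen Plasma (FFP"). For heavier patients, "In patients over 10 kg a pure crystalloid prime will be used".
- **Other products before study drug.** During bypass, "the transfusion trigger for additional units of PRBC will be 7 gm/dL". At the rewarming ROTEM, "Platelets or FFP will be administered at this time, while still on CPB", if a deficiency is shown.
- **Study drug.** "Then immediately after the termination of CPB, RiaSTAP or NS will be administered depending on the group assignment".
- **Analysis.** Statistical Analyses specifies Student's t-test for continuous variables, with no covariates.

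**The concern.** The prime and every on-bypass product are given before the drug, so the drug cannot affect them. If they are part of the tested totals, the comparison carries variance that has nothing to do with treatment. For the prime that variance is driven by body weight, because a fixed volume is divided by weights that run from term newborns to 12-month-olds. FFP is affected directly, and it is one of the two products that the group's own retrospective comparison (Background) found to be reduced. PRBC is affected too. The prime contains no cryoprecipitate or platelets, so it leaves those two unchanged.

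Randomisation prevents systematic bias, but with 15 per arm it does not restore lost precision. Separately, with no fixed start or end, the content of a primary endpoint stays open until the data are in.

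**Working it through.** **The plan's own figure.** N = 30 (15 per group) comes with no SD, effect size or power, so there is no calculation to reproduce. At two-sided 0.05 and 80% power, 15 per arm detects a difference of 1.06 SD (noncentral t).

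**Step 1: size of the prime, from the documents.** FFP prime per kg = 200/weight below 10 kg, and 0 above.

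- 3 kg: 200/3 = 66.7 cc/kg
- 5 kg: 200/5 = 40 cc/kg
- 9.9 kg: 200/9.9 = 20.2 cc/kg

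One FFP dose in the transfusion algorithm is 20 cc/kg, so every infant under 10 kg receives more than one such dose in the prime.

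**Step 2: assumptions.** None of these is in the documents.

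- Weights uniform between *a* and *b* kg, all below 10 kg
- PRBC unit of 300 cc
- Post-drug SD *s* = 20 cc/kg
- True difference 20 cc/kg
- Two-sided alpha 0.05 (the plan gives 0.05 but not the sidedness)
- Correlation *r* between prime and post-drug volume, both in cc/kg, of −0.3, 0 or +0.3
- Prime only; on-bypass doses are not modelled

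**Step 3: SD of the prime.** For prime volume *V*, p = V·√[1/(ab) − (ln(b/a)/(b−a))²]. For 3–9.9 kg and V = 200: 1/29.7 = 0.03367; ln(3.3)/6.9 = 0.17303, squared 0.02994; √0.00373 = 0.0611; p = 12.2 cc/kg. With V = 300, p = 18.3.

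**Step 4: SD of the total.** Total SD = √(s² + p² + 2rsp). At r = 0 and 3–9.9 kg:

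- FFP: √(400 + 149) = 23.4, variance ratio 1.37
- PRBC: √(400 + 336) = 27.1, variance ratio 1.84

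**Step 5: power of the planned t-test** (noncentral t, 15 per arm). Post-drug volume alone, unadjusted: 75%. With the prime counted:

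| Weights | Prime SD, FFP / PRBC | FFP power at r = −0.3 / 0 / +0.3 | PRBC power at r = −0.3 / 0 / +0.3 |
|---|---|---|---|
| 3–9.9 kg | 12.2 / 18.3 | 75 / 62 / 52% | 64 / 50 / 40% |
| 4–7 kg | 6.1 / 9.1 | 79 / 72 / 65% | 78 / 67 / 58% |
| 5–6 kg | 1.9 / 2.9 | 77 / 75 / 73% | 78 / 74 / 71% |

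The loss disappears at r = −p/(2s). For 3–9.9 kg that is −12.2/40 = −0.31 (FFP) and −18.3/40 = −0.46 (PRBC).

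**Step 6: sensitivity at 3–9.9 kg, r = 0.**

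- PRBC power is 56% with a 250 cc unit and 44% with 350 cc.
- FFP power falls from 94% to 78% if the post-drug SD is 15, and from 42% to 37% if it is 30.
- Regaining 75% would take 21 per arm for FFP or 27 for PRBC.

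**Step 7: weight-adjusted analysis.** Simulation, 20,000 trials per cell, linear model with group and weight.

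- Post-drug volume, adjusted: about 73–78% in every weight range and *r* above.
- Prime kept in the total, adjusted: about 71–78%.

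**The case against.** Footnote 12 is a collection list. Its phases stand as separate items beside the component totals, which fits an intention to separate them as well as an intention to pool them. Post-bypass volume may be largely recoverable from data already planned. That is right as far as it goes, and it makes the correction cheap. But no rule says which totals form the endpoint, and the anesthesia total is not split at the end of bypass.

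Total donor exposure is also a legitimate quantity, and the hypothesis speaks of peri-operative transfusion. Restricting to post-drug volume changes what is estimated. This stands, and is a reason to keep total exposure as a separately reported result.

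The power figures rest almost wholly on assumptions; only 200/weight comes from the plan. Even the sign of the effect depends on *r*. At 5–6 kg the loss is at most about 4 points, and a 20 cc/kg difference means a full FFP dose averaged over all patients. With SD 30 and a difference of 10 cc/kg, FFP power is 14% without the prime and 13% with it. The figures are therefore illustrations.

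Adjusting for weight while keeping the prime recovers most of the prime-related loss, so the precision argument favours adjustment more than redefinition. That also stands. Redefinition adds a clear start point and removes on-bypass volume, which was not modelled. Rewarming FFP and platelets add pre-drug noise rather than a 1/weight term if given at the listed per-kg doses; on-bypass PRBC is described in units and so can vary with weight.

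**Conclusion.** The concern holds, as an inexpensive improvement that should be made. The primary transfusion volume has no start at study drug and no single end. Its only breakdown by phase lists prime and on-bypass products, and nothing excludes them. That they enter the tested totals is the natural reading, not a stated rule.

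On that reading the planned unadjusted test loses precision for FFP and PRBC and remains unbiased. At 3–9.9 kg and r = 0, under the assumed SD, difference and PRBC unit, power goes from 75% to 62% (FFP) and 50% (PRBC). Across the weight ranges and correlations tabulated, the effect runs from a gain of about 4 points to a loss of 35 (75% to 40%). The size is uncertain because the documents give no weights, SD, effect or correlation. The recommended analysis holds about 73–78% throughout those scenarios.

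**What to change.** 1. Define the primary transfusion volume, by component (RBC, FFP, platelets, cryoprecipitate), in cc/kg from the start of study drug, or from the bypass stop time already recorded under Schedule of Events footnote 3, to one stated cut-off. One option is 24 hours after surgery, which Transition From Research Participation gives as the end of the study treatment period.
2. Reconcile the peri-operative wording in Endpoints, the hospital-stay wording in Drug protocol and the 24-hour column of the Schedule of Events with that cut-off.
3. Adjust the group comparison for body weight, which is already collected.
4. Report prime, on-bypass, cell-saver and total peri-operative volumes separately.

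The cost is endpoint wording and a little more analysis, with no added patients or procedures. A study-drug timestamp is optional if bypass stop time is used. The primary volume would no longer describe total donor exposure, which item 4 covers. Weight adjustment uses one degree of freedom, about 2 points of power (75% to 73%) if post-drug volume is unrelated to weight.
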